4.2 Exclusion Criteria

Subjects will be excluded from the study if 1 or more of the following criteria are applicable:

1. Prior treatment with trastuzumab, pertuzumab, lapatinib, T-DM1, or other anti-HER2-targeted therapy ≤ 3 weeks before the first dose of ZW25
2. Prior treatment with chemotherapy, other anti-cancer therapy not otherwise specified, or hormonal cancer therapy ≤ 3 weeks before the first dose of ZW25
3. Prior treatment with experimental biologic and non-biologic therapies ≤ 4 weeks before the first dose of ZW25
4. Prior treatment with radiation therapy other than for central nervous system (CNS) disease ≤ 3 weeks before the first dose of ZW25
5. Treatment with anthracyclines within 90 days before first dose of ZW25 and/or total lifetime load exceeding 360 mg/m^2 Adriamycin[®] or equivalent
6. Use of any medications or substances that are strong inhibitors or inducers of CYP3A isoenzymes within 7 days of first dose of any study drug
7. History of life-threatening hypersensitivity to monoclonal antibodies, recombinant proteins, or excipients in the drug formulation
8. Prior treatment with palbociclib or any other CDK4/6 inhibitors, including experimental agents
9. Use of corticosteroids administered at doses equivalent to > 15 mg per day of prednisone within 2 weeks of first ZW25 dosing unless otherwise approved by the sponsor medical monitor. Topical, ocular, intra-articular, intranasal, and/or inhalational corticosteroids are permitted.
10. History of myocardial infarction or unstable angina within 6 months prior to enrollment, troponin levels consistent with myocardial infarction, or clinically significant cardiac disease, such as ventricular arrhythmia requiring therapy, uncontrolled hypertension, or any history of symptomatic congestive heart failure (CHF)
11. QTc Fridericia (QTcF) > 470 ms
12. Grade 2 or greater pneumonitis and/or interstitial lung disease, including pulmonary fibrosis, or other clinically significant infiltrative pulmonary disease not related to lung metastases
13. Active hepatitis B or hepatitis C infection

14. Acute or chronic uncontrolled renal disease, pancreatitis, or severe liver disease (Child-Pugh Class C)
15. Known infection with Human Immunodeficiency Virus (HIV)-1 or HIV-2 (Exception: Subjects with well-controlled HIV [e.g., cluster of differentiation 4 (CD4)-positive T cell count $>350/\text{mm}^3$ and undetectable viral load] are eligible.)
16. Major surgery ≤ 3 weeks prior to the first dose of ZW25
17. Prior or concurrent malignancy whose natural history or treatment has the potential to interfere with the safety or efficacy assessment of the investigational regimen
18. Any other medical, social, or psychosocial factors that, in the opinion of the investigator, could impact safety or compliance with study procedures
19. Females who are breastfeeding or pregnant, and females and males planning a pregnancy
20. Brain metastases: Untreated CNS metastases, symptomatic CNS metastases, or radiation treatment for CNS metastases within 4 weeks of start of study treatment. Stable, treated brain metastases are allowed (defined as subjects who are off steroids and anticonvulsants and are neurologically stable for at least 1 month at the time of screening).
21. Poorly-controlled seizures
22. History of or ongoing leptomeningeal disease (LMD). If LMD has been reported radiographically on baseline MRI, but is not suspected clinically by the investigator, the subject must be free of neurological symptoms of LMD.
23. Grade 3 or greater peripheral neuropathy

4.3 Childbearing Potential

A person of childbearing potential is anyone born female who has experienced menarche and who has not undergone surgical sterilization (e.g., hysterectomy, bilateral salpingectomy, bilateral oophorectomy) or has not completed menopause. Menopause is defined clinically as 12 months of amenorrhea in a person over age 45 in the absence of other biological, physiological, or pharmacological causes.

A person who can father children is anyone born male who has testes and who has not undergone surgical sterilization (e.g., vasectomy followed by a clinical test proving that the procedure was effective).

According to the inclusion and exclusion criteria, pregnant or breast-feeding subjects cannot be included in the study, and adequate contraceptive measures should be taken to prevent female subjects of childbearing potential or female partners of male subjects (either of childbearing potential) from getting pregnant during study participation and for at least 12 months after the last dose of study drug (ZW25, palbociclib, and/or fulvestrant). Subjects will be instructed that known or suspected pregnancy occurring during the study should be confirmed and reported to the investigator. If a female subject is pregnant, the investigator will immediately discontinue the

subject from the study. Upon discontinuation, only those procedures that would not expose the subject to undue risk will be performed.

The investigator should also be notified of pregnancy occurring during the study or within 12 months following last study treatment administration but confirmed after completion of the study.

In the event that a female subject or female partner of a male subject is found to be pregnant after inclusion in the study, the pregnancy will be followed to term with subject/partner consent, and the status of mother and child will be reported to the sponsor after delivery and the status of the baby will be followed for a minimum of 6 months after a live birth.

Details of the pregnancy will be recorded on the withdrawal page of the case report form (CRF), and a Pregnancy Report Form will be completed.

4.4 Removal of Subjects from Therapy or Assessment

The sponsor or their designee must be notified if a subject is withdrawn from study treatment or from the study. The reason(s) for withdrawal must be documented in the subject's medical records and CRF.

4.4.1 Discontinuation of Study Treatment

If any component(s) of the combination therapy is discontinued due to toxicity deemed related to the component(s), subjects on either part of the study may continue to receive the other component(s) of the study regimen until disease progression or start of subsequent anticancer therapy (Note: trastuzumab, alternate CDK4/6 inhibitors, or any other treatment not part of the study regimen will be considered subsequent anticancer therapy. Palliative radiotherapy to a non-target bone lesion that is not progressing is allowed after the second cycle of treatment and must be administered after the initial response assessment obtained per protocol. This will not be considered subsequent anticancer therapy but must not interfere with the assessment of tumor target lesions. Treatment with palbociclib should be interrupted during palliative radiotherapy). Subjects who discontinue treatment with all 3 drugs for any reason (except death or withdrawal of consent) on either part of the study will have an end-of-treatment (EOT) visit within 14 days after the last dose of study drug (ZW25, palbociclib, and/or fulvestrant) and safety follow-up visit at approximately 30 days after the last dose of study drug.

Study treatment may be discontinued for any of the following reasons:

- Adverse event (AE)
- Death
- Lost to follow-up
- Withdrawal of consent
- Physician decision (non-AE, non-progressive disease)
- Pregnancy
- Progressive disease (either radiographic or clinical progression)
- Protocol violation
- Study termination by sponsor
- Other, non-AE

Also, if a subject has not taken ZW25 for more than 4 weeks, he/she will be withdrawn from study treatment unless approval is obtained from the medical monitor to continue on study treatment.

Also, if a subject starts subsequent non-study anticancer therapy, then study treatment will be discontinued before the start of the new therapy

At a minimum, all efforts should be made for subjects to complete the EOT visit ([Section 6.4](#)) and the safety follow-up visit ([Section 6.5](#)), and efficacy ([Section 6.6](#)) and survival follow-ups ([Section 6.7](#)).

4.4.2 Subject Withdrawal from Study

Any subject may be discontinued from the study for any of the following reasons:

- Death
- Lost to follow-up
- Withdrawal of consent
- Study termination by sponsor

5 TREATMENTS

5.1 Treatments Administered

In this study, subjects will be treated with open-label ZW25 in combination with palbociclib plus fulvestrant. Although information for palbociclib and fulvestrant are included in this protocol, in case of conflict between these instructions and the most recent local prescribing information for these approved drugs, Investigators should follow the most recent local prescribing information.

5.2 ZW25

Detailed information describing the preparation, administration, and storage of ZW25 is located in the Pharmacy Manual. Study drug must be diluted as instructed in the Pharmacy Manual prior to administration.

[figure not shown]
On Days 1 and 15 (i.e., ZW25 dosing days) of each treatment cycle, ZW25 will be administered first followed by palbociclib and fulvestrant.

5.2.1 Description of ZW25

ZW25 is a humanized bispecific antibody recognizing 2 non-overlapping epitopes of the ECD of the human HER2 antigen. A schematic representation of ZW25 is shown in [Figure 4](#). The IgG1-like fragment crystallizable (Fc) region of ZW25 contains complementary mutations in each CH3 domain that impart preferential pairing to generate a heterodimeric molecule and correspondingly disfavor formation of homodimers. Chain A is otherwise a normal IgG1 heavy chain and forms a fragment antigen-binding (Fab) arm through pairing with IgG Kappa light Chain A'. Chain A/A' binds to ECD2 of HER2. Chain B has an IgG1-like hinge, CH2 and CH3 domains but contains a single-chain variable fragment (scFv) rather than a Fab arm. Chain B binds to ECD4 of HER2. In place of the constant heavy chain 1 (CH1) domain, it has a variable light (VL) domain, an unstructured 20 amino acid linker of glycine and serine residues, followed

by a variable heavy (VH) domain to form an scFv domain. ZW25 is being developed as a treatment for locally advanced (unresectable) and/or metastatic HER2-expressing cancers.

Figure 4: Structure of ZW25

Fab = fragment antigen-binding; Fc = fragment crystallizable; IgG1 = immunoglobulin G1; scFv = single-chain variable fragment.

5.2.2 Dose and Administration of ZW25

Dosing for ZW25 will be given as follows:

- Part 1:
 - 20 mg/kg IV ZW25; dosing Q2W on Days 1 and 15 of each 28-day cycle. Up to 1 step-down dose level (15 mg/kg Q2W or other dose not lower than 15 mg/kg Q2W) may be evaluated if recommended by the SMC and approved by the sponsor
- Part 2:
 - Recommended dose of ZW25 as confirmed in Part 1 for administration in combination with palbociclib and fulvestrant

Dosing is based on the subject's actual body weight taken at screening visit. Doses must be adjusted for subjects who experience a $\geq 10\%$ change in weight from baseline/ screening visit on dosing day. Subject weight must be measured on all ZW25 dosing days as part of the physical exam (within a window of 3 days prior to dosing). Detailed instructions for dose preparation are provided in the Pharmacy Manual.

ZW25 should be administered prior to any component of the combination chemotherapy regimen. Please refer to the Pharmacy Manual for infusion times. Subjects who experience a Grade 1 or Grade 2 infusion reaction may resume infusion of drug at a reduced infusion rate (50% slower than initial rate). All subjects should receive prophylactic treatment for infusion reactions prior to ZW25 dosing as outlined in [Section 5.2.7.1](#).

5.2.3 Dose Modifications of ZW25

An individual subject who experiences an event that meets the criteria for DLT (defined in [Section 3.1.2](#)) at any time on study treatment may continue at a step-down dose (or an intermediate dose level determined by the SMC) once the toxicity has returned to Grade 1 or baseline with approval of the medical monitor. If the subject then experiences another such event at the step-

down dose level, with approval from the medical monitor, the dose of ZW25 administered to that individual subject should be reduced again but should not go below 10 mg/kg Q2W.

For Part 2 of the study, dose modifications for ZW25-associated toxicity are presented in [Table 5](#) below. Dose decreases or delays for other reasons may be permitted with approval from the medical monitor. The reason for dose decrease or delay must be recorded, and the sponsor must be notified. Up to 2 dose reductions per subject will be allowed for Q2W dosing, but the reduced dose cannot be lower than 10 mg/kg Q2W.

There must be a minimum of 10 days (± 2 days) between doses. Day 15 doses not administered within 6 days after Day 15 must be skipped.

Note: Although only 1 step-down dose level (not lower than 15 mg/kg Q2W) of ZW25 is allowed in the study at a cohort level, individual subjects may have up to 2 dose reductions as long as the reduced dose is not lower than 10 mg/kg Q2W.

Table 5: Recommended Management and Potential Dose Modifications for ZW25-Associated Toxicity

Adverse Event Related to ZW25	Action for ZW25
Grade 1 or Grade 2 nausea and vomiting	
 • Suggest a 5-hydroxytryptamine (5-HT₃) receptor antagonist until resolution of symptoms, or a prochlorperazine. • No dose modification of ZW25 is required. • For breakthrough nausea or vomiting, consider olanzapine 5 or 10 mg daily for three days. For subjects already receiving olanzapine, prochlorperazine may be used.
Grade 3 or Grade 4 nausea and vomiting	
 • Suggest a 5-HT₃ receptor antagonist plus a glucocorticoid especially dexamethasone); consider adding a NK-1 receptor antagonist to a 5-HT₃ receptor antagonist and glucocorticoids if the latter combination is not sufficient for symptom relief. Treatment until resolution of symptoms to \leq Grade 1. • Do not administer ZW25 until severity \leq Grade 1 or pretreatment level. • Optional dose reduction to next lowest dose level after symptoms resolved to \leq Grade 1 or pretreatment level for Grade 3 nausea and vomiting. For Grade 4 symptoms or recurrent Grade 3 symptoms despite maximum use of 5-HT₃ antagonists, glucocorticoids and NK-1 antagonist, dose reduction to the next lowest dose level is mandatory.
Grade 1 or Grade 2 diarrhea	
 • Oral hydration with fluid that contain water, salt and glucose, such as broth or Gatorade. • Suggest loperamide 4 mg PO followed by 2 mg Q4H until no diarrhea. • No dose modification of ZW25 is needed.

Adverse Event Related to ZW25	Action for ZW25
Grade 3 or Grade 4 diarrhea	
 • Aggressive fluid hydration and clear liquid diet. • Suggest loperamide 4 mg PO followed by 4 mg Q2H until resolution of diarrhea; consider octreotide 100 or 150 mcg subcutaneously Q8H for subjects with persistent diarrhea despite 48 hours of loperamide. If subjects are refractory to both loperamide and octreotide, gastroenterologist should be consulted. • For Grade 3 diarrhea, optional dose reduction of ZW25 to next lowest dose level after symptoms resolved to \leq Grade 1 or pretreatment level. For Grade 4 symptoms or recurrent Grade 3 symptoms despite maximum use of loperamide and octreotide, dose reduction is mandatory.
Grade 1 or Grade 2 rash	
 • Suggest topical steroid as needed. • No dose modification of ZW25 is needed.
Grade 3 rash	
 • Suggest initiation with topical steroid; if insufficient, consider oral corticosteroid. Wound care for possible erosion and ulceration to prevent infection, and analgesics for pain control if necessary. • Do not administer ZW25 until severity \leq Grade 1 or pretreatment level. • For Grade 3 rash, optional dose reduction of ZW25 to next lowest dose level after symptoms resolved to \leq Grade 1 or pretreatment level. For Grade 4 symptom or recurrent grade 3 symptom despite maximum use of topic and oral corticosteroid, dose reduction is mandatory.

5-HT3 = 5-hydroxytryptamine; AE = adverse event; NK-1 = Neurokinin-1; PO = orally (per oral); Q2H = every 2 hours; Q4H = every 4 hours; Q8H = every 8 hours

For subjects who cannot receive or tolerate maximal treatment, including dose reduction of ZW25 or refused supportive treatment, study treatment should be permanently discontinued for recurrence of \geq Grade 3 nausea, vomiting, diarrhea or rash.

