The safety of palbociclib (125 mg/day) plus fulvestrant (500 mg) versus placebo plus fulvestrant was evaluated in the PALOMA-3 study (McShane 2018). The data described below reflect exposure to palbociclib in 345 out of 517 subjects with HR-positive, HER2-negative advanced or metastatic breast cancer who received at least 1 dose of palbociclib plus fulvestrant. The median duration of treatment for palbociclib plus fulvestrant was 10.8 months. Dose reductions due to an AE of any grade occurred in 36% of subjects receiving palbociclib plus fulvestrant. No dose reduction was allowed for fulvestrant. Permanent discontinuation associated with an AE occurred in 19 (6%) of 345 subjects receiving palbociclib plus fulvestrant and in 6 (3%) of 172 subjects receiving placebo plus fulvestrant. Adverse reactions leading to discontinuation for subjects receiving palbociclib plus fulvestrant included fatigue (0.6%), infections (0.6%), and thrombocytopenia (0.6%). The most common adverse reactions ($\geq 10\%$) of any grade reported in subjects in the palbociclib plus fulvestrant arm by descending frequency were neutropenia, leukopenia, infections, fatigue, nausea, anemia, stomatitis, diarrhea, thrombocytopenia, vomiting, alopecia, rash, decreased appetite, and pyrexia (IBRANCE®). Rare cases of severe interstitial lung disease/non-infectious pneumonitis, including fatal events, have been reported in subjects treated with palbociclib (Ahsan 2017), (Ahsan 2017), (IBRANCE®), and (Levy 2019). Subjects in the current study ZWI-ZW25-202 will be monitored for potential pulmonary toxicity by routine AE surveillance. Subjects who develop new or worsening respiratory signs or symptoms (e.g., cough, dyspnea, hypoxia, or interstitial infiltrate) will have further palbociclib dosing immediately put on hold and will be urgently evaluated for interstitial lung disease/non-infectious pneumonitis.

The oxidative metabolism of palbociclib is primarily mediated by cytochrome P-450 (CYP). Therefore, a number of medications and foods, including grapefruit products, may interact with palbociclib (McShane 2018). Additional information about prohibited concomitant medications and drug-drug interactions is included in Section 5.3.6 and Section 5.3.7.

Recommended dose modifications are provided in Section 5.3.3.

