A subject will be considered DLT-evaluable if he/she has received $\geq 75\%$ of the planned total dose of each component of study treatment (ZW25, palbociclib, and fulvestrant) over the first 28 days of treatment, and was followed for the full DLT evaluation period, unless the reason for not receiving required doses or not being followed was the occurrence of a DLT. If the reason for not receiving required doses is a DLT, a subject will still be considered evaluable. To account for potential discontinuations prior to being evaluable for DLT (for example, progressive disease [PD] or subject preference), enrollment of replacement subjects will be allowed to permit assessment of DLTs and recommended dose level for Part 2.

Dose-limiting toxicities, defined using the (NCI CTCAE) version 5.0, are events that 1) occur following administration of ZW25, palbociclib, and fulvestrant, or any combination of ZW25 and 1 or more of these drugs; and 2) meet the criteria described below. Events for which there is an alternative clinical explanation (e.g., clearly related to an intercurrent illness, disease progression, or extraneous causes) will not be considered DLTs. The relationship of AEs to each component of study treatment will be determined by the investigator; however, the Sponsor and/or the SMC may query the relationship assessments and/or determine that the event was related to additional components of the regimen.

DLT Criteria Non-Hematologic

Any non-hematologic AE \geq Grade 3 in severity that is not clearly and incontrovertibly due to disease progression or extraneous causes (e.g., accidental injury or similar event) is considered a DLT, with the following exceptions:

- Grade 3 fatigue lasting ≤ 3 days
- Grade 3 diarrhea, nausea, or vomiting that resolves to \leq Grade 1 or baseline within 3 days with adequate supportive care
- Grade 3 rash without maximal use of corticosteroids or anti-infectives
- Infusion reaction \leq Grade 3 (for management of infusion reactions, see [Section 5.2.3.2](#))

Grade 2 or greater events of pneumonitis and/or interstitial lung disease, including pulmonary fibrosis not clearly and incontrovertibly related to disease progression or extraneous causes is considered a DLT.

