3.1.5 Stopping Criteria

If the SMC recommends that the dose of ZW25 needs to be dropped below 15 mg/kg Q2W; the palbociclib dose needs to be reduced below 75 mg; and/or the fulvestrant dose needs to be reduced, then the study may be terminated.

The Sponsor reserves the right to terminate the study at any time for any reason.

For individual subjects, information on study treatment and study discontinuation is provided in [Section 4.4](#). Also, individual subjects may have to discontinue study treatment in case the dose modifications for ZW25 and palbociclib are not sufficient for managing toxicities ([Section 5.2.3](#) and [Section 5.3.3](#)).

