5.3.3 Dose Modifications for Palbociclib and Fulvestrant

For palbociclib, the recommended dose and reduced dose levels for individual subjects (not to be confused with step-down dose levels for subject cohorts) are shown in [Table 8](#).

Table 8: Dose Reduction Levels for Toxicities Associated with Palbociclib

Dose Level	Dose (mg/day on Days 1-21 of a 28-day cycle)
Recommended starting dose	125
First dose reduction	100
Second dose reduction	75

If dose reduction below 75 mg/day is required, then discontinue palbociclib.

Subjects should be monitored for pulmonary symptoms indicative of ILD/pneumonitis. Symptoms may include hypoxia, cough, dyspnea, or interstitial infiltrates on radiologic exams and in whom infectious, neoplastic, and other causes have been excluded by means of appropriate investigations. If new or worsening respiratory symptoms develop or there are other reasons to suspect ILD or pneumonitis, palbociclib dosing should be held while the subject undergoes urgent evaluation. In all subjects diagnosed with \geq Grade 2 pneumonitis and/or interstitial lung disease, including pulmonary fibrosis, palbociclib should be permanently discontinued and the subject taken off of study treatment.

For specific instructions on how to manage other non-hematologic and hematologic toxicities associated with palbociclib, including dose reductions and dose delays, refer to the local prescribing information. On resumption of dosing after a dose delay, every attempt should be made to synchronize palbociclib and fulvestrant with Day 1 of the subsequent cycle.

The fulvestrant dose should be halved (250 mg injections) for subjects with moderate hepatic impairment (Child-Pugh class B). Fulvestrant has not been studied in subjects with severe hepatic impairment (Child-Pugh class C).

For fulvestrant, there are no reduced dose levels for toxicity. If fulvestrant is not tolerated at the recommended dose (or the modified dose for subjects with moderate hepatic impairment), it should be discontinued.

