5.5 Management of Adverse Reactions

Management of infusion reactions and other toxicities related to or associated with ZW25 is described in [Section 5.2.3.2](#). Required premedications as prophylaxis for ZW25 infusion reactions are described in [Section 5.2.7.1](#).

Management of toxicities related to palbociclib and/or fulvestrant is described in [Section 5.3.3](#).

Initial management of adverse reactions should align with treatment measures recommended for the study drug that is most likely responsible for the observed toxicity. For hematological

toxicities (neutropenia, anemia, and thrombocytopenia), infections, and stomatitis palbociclib dose modifications as recommended in local prescribing information should be implemented. Initial management of diarrhea should utilize treatment measures listed for ZW25 in [Table 5 \(Section 5.2.3\)](#). For toxicities that are not common to either palbociclib or ZW25 treatment measures recommended for ZW25, the experimental agent, should be applied first. All study treatments should be permanently discontinued in any subject diagnosed with \geq Grade 2 pneumonitis and/or interstitial lung disease, including pulmonary fibrosis.

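### Section 5.2.3 permits ZW25 to resume after any DLT-level event and does not except Grade 2 or higher pneumonitis/ILD, for which 5.5 and 5.3.3 end all study treatment

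*Combined protocol and SAP*

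**What the plan says.** Section 5.2.3 (Dose Modifications of ZW25) begins with a rule for individual subjects. A subject with an event that meets the 3.1.2 DLT criteria "at any time on study treatment may continue at a step-down dose", or at an intermediate dose set by the SMC, "once the toxicity has returned to Grade 1 or baseline with approval of the medical monitor". If another such event follows at the lower dose, the dose may be reduced again with the monitor's approval, to no less than 10 mg/kg Q2W. No event type is excepted in that paragraph.

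Section 3.1.2 lists among the DLTs "Grade 2 or greater events of pneumonitis and/or interstitial lung disease, including pulmonary fibrosis", unless the event is clearly due to disease progression or an extraneous cause.

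Two sections give a rule specific to that event:

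- Section 5.5: "All study treatments should be permanently discontinued in any subject diagnosed with" Grade 2 or higher pneumonitis or ILD.
- Section 5.3.3: in such subjects "palbociclib should be permanently discontinued and the subject taken off of study treatment".

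Neither provides for resumption with approval.

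**The concern.** The general permission in 5.2.3 takes its scope from the DLT list, and the DLT list contains an event that the protocol elsewhere treats as a permanent stop. Read on its own, 5.2.3 gives the medical monitor authority to approve something that 5.5 and 5.3.3 rule out.

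The stake is subject safety, not inference. The exposed case is a subject whose pneumonitis settles to Grade 1 and who is then given ZW25 again at a lower dose because the site and the monitor consulted the ZW25 dose-modification section and nothing else. A stopping rule for a serious lung toxicity should not depend on each reader noticing a contradiction and resolving it the right way.

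**Working it through.** There is no figure to reproduce and no arithmetic applies. The check sets the sections against one another.

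1. **Does the permission reach pneumonitis/ILD?** Section 5.2.3 covers any event meeting the 3.1.2 criteria, and 3.1.2 names Grade 2 or higher pneumonitis/ILD. Yes, for every such event that is not clearly due to progression or an extraneous cause.

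2. **Is the permission confined to Part 1 or to Cycle 1?** Section 3.1.2 is headed as Part 1 only and the DLT window is 28 days. But 5.2.3 borrows only the criteria and applies them at any time on study treatment, so later cycles are covered, and the sentence is not limited to Part 1.

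3. **Is there an exception elsewhere in the ZW25 section?** Sections 5.2.3 to 5.2.3.3, including Tables 5, 6 and 7, stop ZW25 for some other DLT-level events, such as symptomatic heart failure (Table 6) and Grade 4 infusion reaction (Table 7). None of this text mentions pneumonitis or ILD, and none refers to 5.5.

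4. **Apply both rules to one patient.** Take a subject with Grade 2 pneumonitis, not clearly due to progression, that recovers to Grade 1.

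| Rule | ZW25 | Palbociclib and fulvestrant |
|---|---|---|
| 5.2.3, first paragraph | May resume at a step-down dose if the monitor approves | Not addressed |
| 5.5 | Permanently stopped | Permanently stopped |
| 5.3.3 | Stopped (subject off study treatment) | Palbociclib permanently stopped; subject off study treatment |

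The conflict is confined to the ZW25 column.

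5. **Would another provision catch it?** Section 7.7.2 makes Grade 2 or higher pneumonitis/ILD an adverse event of special interest, so the sponsor is told. That is a report, not a bar on resuming. Section 4.4.1 withdraws a subject who has been off ZW25 for more than 4 weeks unless the monitor approves continuing. A recovery within 4 weeks does not trigger it, and the person who may waive it is the person whose approval 5.2.3 asks for. Both lower the risk; neither removes the contradiction.

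6. **Does anything statistical change?** No. The permission concerns later dosing of an individual subject. The PFS6 definition, the planned enrollment of about 50 in Part 2 and the analysis methods do not depend on which rule is followed.

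**The case against.** The strongest reply is that the protocol already answers the question. The stop is stated twice, in 5.5 and 5.3.3, and the two agree. A specific stop overrides a general and permissive sentence, and a site that stops breaches nothing. An error would need both the site and the monitor to overlook an express rule. All of this stands, and it is why the point is small. It does not make the 5.2.3 sentence correct, because that sentence still confers an authority that the other two sections deny.

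Three stronger readings are tempting, and the documents do not support them.

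- A reader might infer that the ILD rule is hidden from anyone handling toxicity. Section 5.5 does refer readers elsewhere for ZW25 ("Management of infusion reactions and other toxicities related to or associated with ZW25 is described in" 5.2.3.2), but the ILD stop is in that same short section. Section 1.8, which describes the lung risk, points to 5.3.3 for dose modifications. Section 3.1.5, on subjects who may have to discontinue "in case the dose modifications for ZW25 and palbociclib are not sufficient for managing toxicities", cites 5.3.3 as well as 5.2.3. Since 5.3.3 carries the rule, only a reader of 5.2.3 alone is exposed.
- A reader might carry the fatal cases over to this gap. Section 1.8 says: "Rare cases of severe interstitial lung disease/non-infectious pneumonitis, including fatal events, have been reported in subjects treated with palbociclib". That evidence concerns palbociclib. Section 5.2.3 governs ZW25 only and gives no leave to restart palbociclib. For ZW25 safety data the protocol refers to the Investigator's Brochure, which is not among the documents, so nothing can be said here about the risk of ILD recurring on ZW25.
- A reader might see a second defect in the statement, in 4.4.1 and elsewhere, that the other components may continue when one is stopped for toxicity. Sections 5.3.3 and 5.5 already settle that for ILD by ending all study treatment.

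**Conclusion.** The contradiction is real in the current text: for Grade 2 or higher pneumonitis/ILD that recovers, 5.2.3 permits ZW25 with the monitor's approval, while 5.5 and 5.3.3 end all study treatment. Its practical size is small. It is limited to ZW25 re-treatment by a site or monitor relying on 5.2.3 alone, in an event that is also reported to the sponsor. No probability can be attached, because the documents give no rate of pneumonitis/ILD for this combination, and a rate of ILD events would in any case not be a rate of wrongful re-treatment.

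The conclusion assumes that the event-specific rule is what the protocol intends, which the agreement of 5.5 and 5.3.3 supports. It should still be corrected: the toxicity is serious, the two instructions cannot both be followed, and a single clause resolves it.

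**What to change.** Add an exception to the first paragraph of 5.2.3, along these lines:

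> except where this protocol requires permanent discontinuation for the event, including Grade 2 or higher pneumonitis/ILD (Sections 5.3.3 and 5.5), Grade 4 infusion-related reaction (Table 7) and symptomatic heart failure (Table 6). In these cases the event-specific rule governs and the medical monitor may not approve resumption. LVEF decreases are managed per Table 6, including its hold-and-repeat step.

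The LVEF sentence is needed because a blanket bar on resuming after Table 6 events would also block the permitted course of holding ZW25, repeating the LVEF within 4 weeks and discontinuing only if the decline is confirmed or has not recovered. Symptomatic heart failure belongs in the same clause, because it is a cardiac DLT in 3.1.2 and so falls under the same general permission despite the Table 6 stop.

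The cost is this one insertion, by amendment or site clarification letter. No visits, procedures, subjects or analyses are added.
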